6.3 Data Handling Rules

6.3.1 Baseline Values

Baseline values is defined as the values obtained at the most recent assessment prior to the first dose of the study drug. Both scheduled and unscheduled visits will be considered.

Screening values will be considered as the baseline values when the change from screening is of interest.

6.3.2 Study Eye

Each subject’s study eye is defined as the eye that undergoes cataract surgery in the study.

6.3.3 Non-Study Eye

Each subject's non-study eye is defined as the eye that does not have cataract surgery in the study.

6.3.4 Study Day, End of Main Study (EOMS) and End of Sub-Study (EOSS)

Study Day for each subject is calculated relative to the date of the first dose of study drug:

- Study Day = Visit Date/Event Date - Date of First Dose +1
When the Visit Date/Event Date is on or after the Date of First Dose
- Study Day = Visit Date/Event Date - Date of First Dose
When the Visit Date/Event Date is prior to the Date of First Dose

Study Day will be used to define analysis windows for efficacy analyses and to evaluate the timing of events or measurements occurring relative to the first dose of study drug.

Study Day ‘-1’ corresponds to Surgery Day 0 and Study Days ‘-29’ to ‘-2’ correspond to Screening Visit (Days -28 to -1) as shown in the Schedule of Events (Table 2).

EOMS will be either Visit 6/POD22 for all randomized subjects who complete the Main study or the Early Termination/Withdrawal visit for subjects who discontinue the Main study prior to Visit 6/POD22.

EOSS for the subjects in the Endothelial Cell Sub-study will be either Visit 7/POD85 for subjects who complete the Sub-study or the Early Termination/Withdrawal visit for subjects who discontinue the Sub-study prior to Visit 7/POD85.

6.3.5 Analysis Visit for Efficacy Analyses

The use of efficacy data collected in the study will be maximized by including the assessments that are performed outside the planned visit window. Each Analysis Visit (POD 4, 8 and 15) will use an analysis window to determine the efficacy data that will be used to derive the efficacy endpoints. The actual Study Day ([Section 6.3.4](#)) will be used to define the analysis window. The analysis window for each Analysis Visit is shown in Table 3.

Table 3: Analysis Windows for Efficacy Analysis

Analysis Visit	POD4	POD8	POD15
Study Days in Analysis Window	2 – 6	7 – 11	12 – 17 or Scheduled Visit*

* Only for subjects who (i) complete at least 14 days of dosing, (ii) do not use rescue medication and (iii) have a scheduled POD15 visit after Study Day 17.

If the efficacy assessments are performed at unscheduled visits occurring after Visit 2/POD1 and before Visit 5/POD15, the date of the unscheduled visits will also be used to determine the appropriate analysis window.

The efficacy assessments performed after two days following the last dose of study drug will not be used when the subjects have administered less than 14 days of study drug.

When multiple efficacy assessments fall within the same analysis window for an Analysis Visit (see Table 3), the following rules will be applied:

- If two scheduled assessments fall within the same analysis window for an Analysis Visit and one of the Analysis Visits (either before or after the Analysis Visit with two scheduled assessments) has no scheduled assessment, then the scheduled assessment data will be used for the Analysis Visit without an assessment. For example, when a subject has a scheduled POD4 visit at Study Day 3 and a scheduled POD8 visit at Study Day 6, the Analysis Visit POD4 would have two scheduled assessments and the Analysis Visit POD8 would have no data. In this case, the scheduled POD8 visit assessments will be used for the Analysis Visit POD 8.
- If one scheduled assessment and at least one unscheduled assessment fall within the same analysis window for an Analysis Visit, the latest value in the analysis window will be used for all relevant efficacy analyses.

The definition of the analysis window for each Analysis Visit for the efficacy analyses will be re-examined prior to database lock. If there is a need to adjust the analysis window in Table 3, the SAP will be amended to document the changes.

6.4 Statistical/Analytical Issues

6.4.1 Adjustments for Covariates

The analysis of the continuous secondary efficacy endpoints will be adjusted for baseline values as a covariate in the analyses of covariance (ANCOVA).

6.4.2 Rescued Subjects

Any subject not responding to the study drug because of lack of efficacy at any time after randomization at Visit 2/POD1 may be rescued and placed on an appropriate alternative therapy determined by the Investigator.

The efficacy assessments performed after starting rescue medication will be excluded from the efficacy analyses.

For the primary efficacy endpoints, subjects who are rescued at any time after the first dose of study drug and before the efficacy assessments at POD15 will be considered as treatment failures (Non-responders). The same approach will be applied to derive the secondary endpoint of sustained ACF grade =0.

For both categorical and continuous secondary efficacy endpoints of ACC grade, ocular pain grade and ACF grade, the last observation carried forward (LOCF) approach will be used to impute the data for each Analysis Visit after starting rescue medication.

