The primary efficacy analyses to compare APP13007 against placebo will be conducted on the Intent-To-Treat (ITT) population using the Pearson Chi-square statistic. Fixed sequence testing will be employed to maintain the 2-sided alpha = 0.05. The primary analyses will first test the difference in the proportion of subjects with ACC count = 0 (Grade = 0) at POD8 (Visit 4) maintained through POD15 (Visit 5) between treatment groups. If the test is statistically significant at the 2-sided alpha = 0.05 level in favor of APP13007, the difference in the proportion of subjects with Ocular Pain Grade = 0 at POD4 (Visit 3) maintained through POD15 (Visit 5) between treatment groups will be tested at the two-sided alpha = 0.05 level.

Analyses of Secondary Efficacy Endpoints:

Mean change-from-baseline in ACC Grade, Ocular Pain Grade, ACF Grade and visual acuity at PODs 4, 8 and 15 will be analyzed using an analysis of covariance (ANCOVA). The ANCOVA model will include treatment as a fixed effect and baseline as a covariate. The rest of the secondary efficacy endpoints will be analyzed using the same method described for the primary efficacy endpoints. Rescued subjects will be considered to be treatment failures.

Safety Analysis:

The safety analysis will summarize ocular treatment emergent AEs (TEAEs) in the study eye and ocular AEs for the non-study eye. Ocular and non-ocular TEAEs will be summarized similarly.

The other safety endpoints, including corneal endothelial cell parameters (corneal endothelial cell density, percent hexagonality and coefficient of variation) will be summarized as discussed in the Statistical Considerations section of the protocol.

STUDY DESIGN

Figure 1: Study Schematic

[figure not shown]

Table 1: Schedule of Events

PROCEDURE/ASSESSMENTS ¹	Visit 1 Screening (Day -28 to -1)	Surgery ² Day 0	Visit 2 POD1 ³	Visit 3 POD4 (±1 Day)	Visit 4 POD8 (±1 Day)	Contact POD14	Visit 5 POD15 (+1 Day) ⁴	Visit 6 POD22 (±2 Days) ⁵	Reminders (~POD50 and ~POD78)	Visit 7 POD85 (±4 Days) ⁶
ICF, Demography, Medical History	X									
Determine Eligibility, Review Inclusion/Exclusion Criteria	X		X							
Urine pregnancy test only for women of child-bearing potential			X				X			
Ocular Symptoms Assessment ⁷	X		X	X	X		X	X		
ETDRS Visual Acuity	X		X	X	X		X	X		
Slit Lamp Biomicroscopy ⁸	X		X	X	X		X	X		
Indirect Ophthalmoscopy (dilated)	X							X		
IOP (Goldmann applanation tonometry) ⁹	X		X	X	X		X	X		
Corneal Endothelial Cell Parameters ¹⁰	X							X		X

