10.3.2 Analysis of Efficacy

All efficacy analyses and summaries will be based on assessments in the study eye for each subject.

Subjects who are rescued at any time prior to Visit 5 (POD15) will be considered as treatment failures for the primary efficacy endpoints and the relevant secondary efficacy endpoints. For subjects who discontinue from the study prior to Visit 5 (POD15), the last observation carried forward (LOCF) approach will be used to impute missing data.

For continuous secondary efficacy endpoints, the LOCF approach will also be used to impute the data at visits after subjects are rescued.

The ACC count will be graded as shown below:

Grade	0	1	2	3	4
ACC Count	0 cell	1-5 cells	6-15 cells	16-30 cells	> 30 cells

10.3.2.1 Analyses of Primary Efficacy Endpoints:

The primary efficacy analyses to compare APP13007 against placebo will be conducted on the ITT population using the Pearson Chi-square statistic. Fixed sequence testing will be employed to maintain the 2-sided alpha = 0.05. The primary analyses will first test the difference between treatments in the proportion of subjects with ACC count = 0 (Grade = 0) at POD8 (Visit 4) maintained through POD15 (Visit 5). If the test is statistically significant at the 2-sided alpha = 0.05 level in favor of APP13007, the difference between treatments in the proportion of

subjects with Ocular Pain grade = 0 at POD4 (Visit 3) maintained through POD15 (Visit 5) will be tested at the two-sided alpha = 0.05 level.

To confirm the robustness of primary analysis results, sensitivity analyses, including using observed data from all subjects, will be performed. The detailed sensitivity analyses will be described in the SAP.

10.3.2.2 Analyses of Secondary Efficacy Endpoints:

Mean change-from-baseline in ACC Grade, ocular Pain Grade, ACF Grade and visual acuity at PODs 4, 8 and 15 will be analyzed using an analysis of covariance (ANCOVA). The ANCOVA model will include treatment as a fixed effect and baseline as a covariate. The rest of secondary efficacy endpoints will be analyzed using the same method described for the primary efficacy endpoints.

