10.2.2 Analysis of Secondary Efficacy Endpoints

10.2.2.1 Analysis of Categorical Endpoints of ACC, Ocular Pain and ACF

The secondary efficacy endpoints (categorical endpoints) of ACC grade, Ocular Pain grade and ACF grade will be analyzed and summarized in the same manner as described for the primary efficacy endpoints ([Section 10.1.2](#)). The imputation for missing values for the categorical endpoints is described in [Section 6.4.3.1](#). The proportion of subjects with ACC grade = 0, Ocular Pain grade = 0, and ACF grade = 0 at PODs 4, 8, and 15 will be plotted separately for each of these endpoints.

In addition, the ACC grade, Ocular Pain grade and ACF grade will be tabulated, including the number and percentage of subjects in each grade category, using the observed data only.

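### For the by-visit grade 0 endpoints the SAP carries the last pre-rescue value forward, so a rescued subject can count as a success at later visits; the protocol text points to treatment failure

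*SAP*

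**What the plan says.** **Protocol.** Section 10.3.2 states that subjects rescued before Visit 5 "will be considered as treatment failures for the primary efficacy endpoints and the relevant secondary efficacy endpoints". It then gives a separate rule for one type of endpoint: "For continuous secondary efficacy endpoints, the LOCF approach will also be used to impute the data at visits after subjects are rescued". Secondary endpoints not analysed by ANCOVA follow the primary method: "The rest of secondary efficacy endpoints will be analyzed using the same method described for the primary efficacy endpoints". In the synopsis, the paragraph on secondary endpoints ends without any qualifier: "Rescued subjects will be considered to be treatment failures". Sections 5.4.1, 8.1.1 and 9.4.2 also describe rescued subjects as treatment failures.

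**SAP.** Section 6.4.2 removes post-rescue data: "The efficacy assessments performed after starting rescue medication will be excluded from the efficacy analyses". It makes rescue before the POD15 assessments a non-response on the two primary endpoints, and extends this to one secondary endpoint: "The same approach will be applied to derive the secondary endpoint of sustained ACF grade =0". For the other secondary endpoints on these three signs, the rule at visits after rescue is "For both categorical and continuous secondary efficacy endpoints of ACC grade, ocular pain grade and ACF grade, the last observation carried forward (LOCF) approach". Section 6.4.3.1 repeats this for subjects who are rescued and then leave the study. The value carried is the last one after first dose and before rescue. Non-responder applies to the categorical endpoints only when there is nothing to carry. Section 10.2.2.1 says that the categorical endpoints "will be analyzed and summarized in the same manner as described for the primary efficacy endpoints".

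**The concern.** The endpoints concerned are the proportions with ACC, ocular pain and ACF grade 0 at POD4, POD8 and POD15. The rule matters at POD8 and POD15, which gives six results (three signs at two visits) and their plots. At those visits the success count can include subjects who have stopped study drug and started alternative therapy.

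Success then means different things in different tables of the same report. A reader would expect a by-visit responder rate to treat rescue as the primary endpoint does, the more so because SAP 10.2.2.1 promises the same manner of analysis. The protocol text supports that expectation, and the SAP does not flag a departure from it.

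**Working it through.** **1. The plan's own figures.** The documents give no rescue rate, no by-visit rate and no share of rescued subjects at grade 0, so there is no planned figure to reproduce on this point. The sample-size figures do reproduce. For 26% v 12% at two-sided 5% and 92% power, n = 176 per arm (stated 175). Power at 175 is 91.9% for ACC and 94.8% for pain (57% v 38%). With dropout, 175/0.95 = 184.2, so 185 per arm. These concern the primary endpoints and do not change.

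**2. The rules side by side.**

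| Endpoint | Protocol after rescue | SAP after rescue |
|---|---|---|
| Two primary endpoints | failure | Non-responder |
| Sustained ACF grade 0 | failure, if *relevant* | Non-responder |
| By-visit grade 0 (ACC, pain, ACF) | failure, if *relevant*; LOCF not given | LOCF |
| Mean change in ACC, pain, ACF grade | LOCF | LOCF |

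The documents part in the third row.

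**3. Can a rescued subject be a success?** Yes, if the last pre-rescue grade on that sign was 0. Protocol 9.4.1 makes this plausible. Its quantitative criteria concern cells and flare, not pain, and it foresees rescue for pain or photophobia while cells or flare improve.

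- *Pain.* A subject has pain 0 at the POD4 visit and is rescued on Study Day 5 for a rise in cells. On the primary pain endpoint this is a Non-responder. By visit, the subject is a pain success at POD8 and POD15. One condition applies. Study Day 5 lies in the POD4 window (days 2-6), and SAP 6.3.5 takes the latest value when a scheduled and an unscheduled assessment share a window. The trace therefore holds only if pain was still 0, or was not assessed, at the rescue visit before rescue started.
- *Flare.* A subject has ACF 0 at POD4 and is then rescued for pain, with ACF still 0 or not reassessed. By visit, this is an ACF success at POD8 and at POD15. On ACF 0 at POD8 maintained through POD15, the same subject is a Non-responder.

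**4. Possible size.** Let r be the rescue rate in an arm, and f the share of all rescued subjects whose last pre-rescue grade on the sign was 0. The SAP rule raises that arm's success rate by r x f, and the treatment difference narrows by (r x f on placebo) - (r x f on APP13007).

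Assumed inputs, none from the documents: r = 20-40% on placebo, r = 5-15% on APP13007, f = 20-40%.

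- Placebo rises by 0.20 x 0.20 = 0.04 to 0.40 x 0.40 = 0.16. At 185 per arm that is 7.4 to 29.6 subjects.
- APP13007 rises by 0.05 x 0.20 = 0.01 to 0.15 x 0.40 = 0.06, or 1.9 to 11.1 subjects.
- Narrowing with the same f in both arms: (0.20 - 0.15) x 0.20 = 0.01 to (0.40 - 0.05) x 0.40 = 0.14.
- Narrowing with f free to differ by arm: 0.20 x 0.20 - 0.15 x 0.40 = -0.02 to 0.40 x 0.40 - 0.05 x 0.20 = 0.15. At the lower end the difference widens.
- Equal r and f in both arms: both rates rise and the difference does not move. With r = 10% and f = 10-50%, each rate rises by 1 to 5 points.

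Subtracting low from low and high from high (0.04 - 0.01 and 0.16 - 0.06) would give 3 to 10 points, but that leaves out combinations which the same assumptions allow.

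**5. Does another planned analysis cover it?** No. SAP 10.1.3 and 10.1.4 concern the primary endpoints only. The observed-data grade tabulation in 10.2.2.1 omits post-rescue values and does not count them as failures.

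**The case against.** **The protocol is not explicit.** It never says which secondary endpoints are *relevant*, and section 10.1 leaves analysis detail to the SAP. The SAP could be read as narrowing the word to sustained ACF. This stands in part. It does not explain why the protocol limits post-rescue LOCF to continuous endpoints, or why the synopsis sentence has no qualifier.

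**The rule was intended.** The SAP's summary of changes says that the LOCF approach for secondary endpoints was clarified in response to FDA comments on SAP v1.0. This stands, and the rule should not be called a slip. A reader might infer that the FDA asked for LOCF on responder endpoints. The documents do not say so, and the comments are not reproduced.

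**Much of the effect can be seen.** The primary table format, applied to these endpoints, separates responders with imputed data from those without, and SAP 10.2.2.3 gives cumulative rescue counts by visit. This also stands in part. The imputed-responder row pools rescue with other missing data, so the rate with rescue as failure cannot be read off.

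**The stakes are limited.** These endpoints lie outside the fixed sequence, which covers the two primary endpoints only. If rescue is commoner on placebo, the rule tends to be conservative. This stands. A reader might infer a bias in favour of APP13007, but nothing in the documents supports that direction.

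**Conclusion.** The conflict holds for the by-visit grade 0 endpoints of ACC, pain and ACF. Under SAP 6.4.2 and 6.4.3.1 a rescued subject counts as a success at later visits when the last pre-rescue grade on that sign was 0. The protocol text points to failure, with real ambiguity in the word *relevant*.

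Its size cannot be known from the documents. On the assumed rescue rates and a common grade 0 share, the by-visit difference shifts by about 1 to 14 points, usually toward a smaller difference if rescue is more frequent on placebo. With shares free to differ by arm, the range is about -2 to +15 points, so even the direction is not fixed.

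Two stronger readings fail. A reader might infer that every rescued subject becomes a by-visit success; only those last seen at grade 0 do. A reader might also infer that the main efficacy claim is affected; both primary endpoints, and sustained ACF grade 0, count rescue as non-response. What is at issue is the meaning of the by-visit rates and their agreement with the protocol.

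**What to change.** In SAP 6.4.2, 6.4.3.1 and 10.2.2.1:

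- Add an analysis of the proportions with ACC, pain and ACF grade 0 in which every Analysis Visit after the start of rescue is Non-responder, and report it beside the LOCF version. State the timing rule in words, because protocol 10.3.2 does not say how failure maps to single visits.
- State which endpoints are the *relevant* secondary ones.
- Keep the LOCF version, given its link to the regulator's comments, but document it as a departure from the protocol text and give the reason.

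The cost is SAP wording and one extra set of columns. Rescue start dates are already needed for the primary endpoints, so no new data are collected.

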6.4.3 Handling Dropouts or Missing Data

6.4.3.1 Imputation of Missing Efficacy Data

The missing data handling rule for the study eye will be applied for the efficacy endpoints.

Missing data from subjects who discontinue the study before POD15 assessments without taking rescue medication:

For subjects who prematurely discontinue the study without taking rescue medication, the LOCF approach will be used to impute the missing data. The last observation will be the last assessment value after the first dose of study drug and up to two days following the last dose of study drug.

Missing data from subjects who discontinue the study before POD15 assessments and take rescue medication before POD15 assessments:

For both categorical and continuous secondary efficacy endpoints of ACC grade, ocular pain grade and ACF grade, subjects who take rescue medication before POD15 assessments and prematurely discontinue the study, the LOCF approach will be used to impute the missing data. The last observation will be the last assessment value after the first dose of study drug and prior to starting rescue medication.

Intermittent missing data:

The likelihood of having intermittent missing data is low. For subjects with intermittent missing data for efficacy endpoints, the LOCF approach will be applied to impute the missing data, i.e., using the data collected from the most recent prior visit after the first dose of study drug.

If no data can be carried forward (i.e., missing assessments at POD 4 visit or no available post-baseline assessments), missing data will be treated as missing for the continuous endpoints and will be considered as 'Non-responder' for the categorical endpoints.

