10. EFFICACY ANALYSES

All efficacy analyses will be performed using the ITT population. In addition, analyses of the primary efficacy endpoints will be performed using the PP population as a sensitivity analysis. All efficacy analyses and summaries will be based on assessments in the study eye for each subject.

The data for subjects who are rescued at any time after the first dose of study drug and before the efficacy assessments at POD15 will be handled as described in [Sections 6.4.2](#) and [6.4.3.1](#). The data for subjects who prematurely discontinue the study without taking any rescue medications will be handled as described in [Section 6.4.3.1](#).

The Analysis Visits (PODs 4, 8 and 15) defined in [Section 6.3.5](#) will be employed in the efficacy analyses.

Baseline values for the efficacy endpoints are defined as the assessment values obtained at POD1 pre-dose.

All efficacy data will be presented in listings.

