10.2.2.2 Analysis of Continuous Endpoints of ACC, Ocular Pain, ACF and BCVA

Mean change from baseline in ACC grade, Ocular Pain grade, ACF grade and BCVA at PODs 4, 8 and 15 will be analyzed using an analysis of covariance (ANCOVA). The ANCOVA model will include treatment as a fixed effect and baseline as a covariate. The imputation for missing values for the continuous endpoints is described in [Section 6.4.3.1](#).

The values of the endpoints and change from baseline at PODs 4, 8 and 15 will be summarized by treatment group using descriptive statistics, including 95% CI for the mean of the change-from-baseline. The adjusted mean of the change from baseline and the treatment difference of adjusted means with associated 95% CI from ANCOVA will be presented. The mean change from baseline with 95% CI at PODs 4, 8 and 15 will be plotted.

In addition, the ACC grade, Ocular Pain grade, ACF grade and BCVA, and change from baseline will be summarized descriptively using the observed data only.

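### SAP 6.4.2 and 6.4.3.1 leave BCVA out of the post-rescue LOCF rule that the protocol applies to all continuous secondary endpoints, so rescued subjects fall out of the later BCVA comparisons

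*SAP*

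**What the plan says.** The protocol's rule is general. Section 10.3.2 states: "For continuous secondary efficacy endpoints, the LOCF approach will also be used to impute the data at visits after subjects are rescued". It makes no exception for visual acuity, and Section 10.3.2.2 places visual acuity among the ANCOVA endpoints: "Mean change-from-baseline in ACC Grade, ocular Pain Grade, ACF Grade and visual acuity at PODs 4, 8 and 15 will be analyzed".

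The SAP splits the rule in two. Section 6.4.2 first removes data: "The efficacy assessments performed after starting rescue medication will be excluded from the efficacy analyses". That sentence covers all efficacy endpoints, BCVA included. The same section then brings back imputed values for "secondary efficacy endpoints of ACC grade, ocular pain grade and ACF grade, the last observation carried forward (LOCF) approach will be used". BCVA is not in that list.

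Section 6.4.3.1 uses the same list for rescued subjects who go on to leave the study: "For both categorical and continuous secondary efficacy endpoints of ACC grade, ocular pain grade and ACF grade, subjects who take rescue medication before POD15 assessments". Its rule for leaving without rescue is not limited by endpoint: "For subjects who prematurely discontinue the study without taking rescue medication, the LOCF approach will be used to impute the missing data".

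SAP 10.2.2.2 specifies the BCVA ANCOVA together with those for ACC, pain and flare grade. On imputation it says only "The imputation for missing values for the continuous endpoints is described in" Section 6.4.3.1. SAP 10 sets the population: "All efficacy analyses will be performed using the ITT population".

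**The concern.** Three of the four continuous secondary endpoints have a complete rule after rescue: drop the observed value and carry forward the last one before rescue. The fourth, BCVA, has only the first half. A rescued subject then has no BCVA value at later visits and leaves those ANCOVAs, whereas the protocol would keep that subject in with a carried-forward value.

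Rescue is prompted by lack of efficacy, so it is not a random reason for absence. If rescued eyes differ in acuity and rescue is more frequent in one arm, the subjects left at POD8 and POD15 are no longer comparable between arms in the way randomization intended.

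Nothing elsewhere in the SAP makes up for the loss. The observed-data summary in 10.2.2.2 does not lift the exclusion in 6.4.2. The safety tables for BCVA in 11.3.2 also leave out scores obtained after rescue. Post-rescue acuity would appear only in listings, although rescued subjects stay in the study and continue to be measured.

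**Working it through.** The documents state no figure for the BCVA analysis, so there is none to reproduce. The check is mainly a comparison of rules.

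**1. Which rule reaches a rescued subject's BCVA?**

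| Rule | ACC, pain, ACF grade | BCVA |
|---|---|---|
| Protocol 10.3.2, after rescue | LOCF | LOCF |
| SAP 6.4.2, values observed after rescue | excluded | excluded |
| SAP 6.4.2, imputation after rescue | LOCF | not named |
| SAP 6.4.3.1, rescued and then discontinued | LOCF | not named |
| SAP 6.4.3.1, discontinued without rescue | LOCF | LOCF, but does not apply to rescued subjects |
| SAP 6.4.3.1, intermittent gaps | LOCF | LOCF, but written for occasional missed visits |

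**2. What happens visit by visit?**

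| Time of rescue | BCVA under the protocol | BCVA under the SAP as written |
|---|---|---|
| Before any post-baseline assessment | nothing to carry forward; missing | missing |
| At POD4, after that visit's assessments | POD4 observed; POD8 and POD15 carried forward | POD4 observed; POD8 and POD15 absent |
| Between POD8 and POD15 | POD15 carried forward | POD15 absent |
| At Visit 5 | all observed | all observed |

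The last row follows from Protocol 9.4.2, which requires the Visit 5 assessments to be completed before rescue medication is given. The first row follows from the end of SAP 6.4.3.1.

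**3. How many subjects could be lost?** The documents give about 185 randomized per arm (Protocol 10.4) but no rescue rates. The rates below are assumptions. Retained = 185 × (1 − rate), rounded.

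| Assumed rescue by POD15, active / placebo | Retained at POD15, active / placebo | Lost of 370 |
|---|---|---|
| 2% / 10% | 181 / 166 | 23 |
| 5% / 20% | 176 / 148 | 46 |
| 5% / 30% | 176 / 130 | 64 |
| 10% / 40% | 166 / 111 | 93 |

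These counts are upper limits on the departure from the protocol. Subjects rescued at Visit 5 are not lost, and those with no post-baseline value before rescue would be missing under the protocol as well. At POD8 only rescues before that visit count.

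**4. What would the loss do to the estimate?** Let r be an arm's rescue rate and g the amount by which rescued eyes are worse in logMAR, taken as equal in both arms. An arm's full mean equals its non-rescued mean plus r × g. Dropping rescued subjects therefore shifts the between-arm difference by (placebo r − active r) × g.

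- g = 0: no shift at any rescue rates.
- 20% against 5%, g = 0.1: 0.15 × 0.1 = 0.015 logMAR, or 0.75 letter at 0.02 per letter.
- 30% against 5%, g = 0.2: 0.25 × 0.2 = 0.05 logMAR, or 2.5 letters.
- g negative, for example if rescue therapy works well: the sign reverses.

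This formula compares dropping rescued subjects with including their actual values, and it ignores the ANCOVA's baseline adjustment. It does not compare dropping with LOCF. That contrast depends on how far acuity had recovered by the last visit before rescue, which the documents do not allow one to calculate.

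**The case against.** The strongest reply is that the SAP never says BCVA is left unimputed. Section 10.2.2.2 sends the continuous endpoints to 6.4.3.1, which opens by addressing efficacy endpoints generally and has an intermittent-missing rule not tied to any endpoint. A programmer who knows the protocol could carry BCVA forward on that basis. This stands in part: the wording leaves room for it. But the intermittent rule is written for gaps the SAP calls unlikely, not for every visit after a rule-based exclusion, and it does not say that the carried value must precede rescue. At best, two competent programmers could analyse different sets of subjects.

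A reader might infer three stronger things, none of which the documents support.

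- That the BCVA analysis becomes a single analysis of never-rescued subjects. It does not: the loss is visit by visit.
- That the error works against the drug by a known amount. That needs rescue rates and an acuity gap, and neither is given.
- That the ITT statement in SAP 10 is broken. ITT defines who belongs to the population; a missing value at a visit does not by itself contradict it, and 6.4.3.1 openly leaves some continuous values missing.

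It is also fair to say that the omission might be deliberate. The SAP's summary of changes says the LOCF approach for secondary endpoints was clarified after regulator comments. Those comments are not available, and the summary mentions neither BCVA nor a departure from the protocol. Intent cannot be judged either way.

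**Conclusion.** The conflict between the two documents is real and rests on their text alone. The protocol carries BCVA forward after rescue. The SAP, read as written, excludes it and supplies no replacement, so each BCVA ANCOVA uses only subjects not yet rescued at that visit.

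The comparison can be biased if rescue is related to acuity and differs by arm. The size and direction of any bias are unknown: the counts and shifts above rest wholly on assumed rates and an assumed acuity gap, and the shift is zero if rescue is unrelated to acuity. The consequence is limited. BCVA change is one secondary endpoint outside the fixed-sequence test, so the two primary tests and the sample size are untouched. The gap should be closed before database lock, but it does not threaten the trial's main conclusions.

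**What to change.** 1. Add BCVA to the post-rescue LOCF sentence in SAP 6.4.2 and to the matching sentence in 6.4.3.1, so that both agree with Protocol 10.3.2. If another treatment of BCVA is intended, state it and justify it as a departure from the protocol.
2. Report the number of subjects in the BCVA ANCOVA by arm and visit, separating observed from carried-forward values.
3. Add a sensitivity analysis of BCVA change on all observed values, including those after rescue. State that for this analysis the post-rescue exclusion in 6.4.2 is set aside, and so is the limit in 6.3.5 on assessments made more than two days after early stopping of study drug. SAP 10.1.4 already uses post-rescue data in this way for the primary endpoints.

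The cost is a few words in the SAP and one additional table. No new data are needed, because rescued subjects remain in follow-up and their acuity is already scheduled to be measured.
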